11.1 Adverse Experience Reporting

Study staff will monitor participants and be alert to any adverse events at each study.. Testers and Trainers will ask participants about any adverse events at the end of each testing and intervention visit. Furthermore, the participants will be interviewed about any such events throughout their study participation at the post-test visit. Study staff will be alert to any volunteered adverse events. All such events will be documented on a standardized form. At all in-person contacts and at any other applicable time throughout the study, any potential adverse events reported by a subject or observed by the research staff will be recorded and subsequently evaluated by the Principal Investigator for its relation to the study research procedures and whether or not any corrective action need be taken. It is unlikely and not expected that any adverse incident will result from implementation of this study protocol. However, any and all adverse events that may occur will be recorded on the appropriate forms, and reported to the governing IRB, as applicable.

Any adverse events will be reported to the site IRB within 72 hours of occurrence or detection by PI [name]. In the unlikely event of a serious adverse event this report will be made within 24 hours and reported also to the NIH Project Officer. In the unlikely case of study-related serious adverse events, an interim analysis will be performed in order to determine whether a change in the risk/benefit ratio has occurred and reviewed by the statistician [name]. If so, this change will be brought to the attention of the USF IRB for review, current and future participants will be notified of this change, and stopping rules will be considered.

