6.1.3 Post-Test

At the post-test visits, cognition-,CAP- and everyday function outcome measures will be re-administered by blinded Research Assistant Testers. Participants will complete the CAP, cognition, and everyday function measures administered at baseline. Alternative forms will be used, as available. The Tester will complete a form indicating whether or not they know the randomized condition of the participant to assess success of blinding and will confirm continued eligibility. A questionnaire will be administered to check for adverse events during the course of the study. Participants will be encouraged to complete post-test regardless of adherence. We will attempt to complete post test for up to 60 days after the training completion date (≥ 16 sessions completed) or 18 weeks post baseline if intervention was not attempted or completed. Participant post-tests will be conducted after the intervention phase for those who complete between 1-15 sessions.⁶

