6.3 Intervention Discontinuation Evaluations Retention

A CONSORT chart will be completed at the end of the trial. Participant status (e.g., screened, enrolled, refused, ineligible) will be recorded at each assessment. Reasons for ineligibility will be documented.

We will employ an intent-to-treat design as detailed in section 9.5 below. Participants who discontinue intervention will be encouraged to complete study visits and we will make every effort to follow and evaluate all enrolled participants.

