Participants who miss an in-lab training session unexpectedly (i.e., without having a make-up session scheduled) will be contacted by the Research Assistant Trainer or lab staff within 3 days of the missed session. Participants will be requested to schedule a make-up in-lab training session as soon as possible. Participants will be reminded that their goal is to complete 20 sessions before post-test I visit. We will further encourage the participant to return for their post-test assessment visit regardless of training adherence. If we do not successfully make contact with the participant within the first three days, we will continue to attempt to contact them 2-3 times per week for three weeks. If we are still unable to reach the participants, we will send a letter requesting a reply. Secondary contact individuals will be approached if we lose contact with the enrolled study participant with no response to phone calls or a letter after repeated attempts over a 90-day period.

If participants are finding it difficult to attend the in-lab sessions, we will allow up to three sessions of training to be completed each week (1 session per 24 hours) until the intervention phase has ended or 15 weeks have passed since training began.

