7 MANAGEMENT OF ADVERSE EVENTS

We will track safety throughout the trial. Participants will be queried as to whether or not they experienced any discomfort at the end of each study visit. See **Reporting of Adverse Events** below for further details. Data and safety monitoring will focus on participant recruitment, data quality, and safety (confidentiality, minimization of risks, and surveillance for adverse events). The study team will meet weekly to discuss the progress of the trial. Details on adverse event monitoring and reporting are provided below.

An adverse event (AE) is defined as any unfavorable and unintended diagnosis, symptom, sign, syndrome or disease which either occurs during the study, having been absent at baseline, or if present at baseline, appears to worsen. Adverse events are to be recorded regardless of their relationship to the study intervention.

Participants may experience fatigue or frustration from completing the intervention exercises. Prolonged sitting activity can result in muscle/joint soreness (e.g., wrist, elbow, fingers, hip flexors, neck, back, buttock), eye strain, muscle cramping or stiffness, or headaches. Any of these symptoms that increase in frequency and last more than 24 hours after participating in intervention exercises will be considered an adverse event. The participant will be advised to seek treatment and not be continued until a physician clears such activity. Serious adverse effects from prior research of the interventions have not been reported.

A serious adverse event (SAE) is generally defined as any untoward medical occurrence that results in death, is life threatening, requires inpatient hospitalization or prolongation of existing hospitalization, results in persistent or significant disability/incapacity.

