11.2 Follow-up for Adverse Events

Research Assistants will monitor participants for any adverse events at study visits. At the post-test study visit, participants will be directly interviewed about any possible adverse events that occurred since their initial visit. A study physician and/or [name] will follow-up with the participant for any adverse events. The participant will be referred to proper treatment.

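### No adverse-event question is planned after the last attended session for a participant who stops training voluntarily and then misses post-test

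*Combined protocol and SAP*

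**What the plan says.** Active questions about harm occur at two kinds of contact.

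- **Attended visits.** Section 7: "Participants will be queried as to whether or not they experienced any discomfort at the end of each study visit". Section 11.1: "Testers and Trainers will ask participants about any adverse events at the end of each testing and intervention visit".
- **Post-test.** Section 6.1.3: "A questionnaire will be administered to check for adverse events during the course of the study". Section 11.2: "At the post-test study visit, participants will be directly interviewed about any possible adverse events that occurred since their initial visit".

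The Schedule of Evaluations in section 6 agrees: the adverse-event row is marked at baseline, clinical evaluation, intervention and post-test, and nowhere else.

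Outside visits, capture is passive. Section 11.1: "Study staff will be alert to any volunteered adverse events". The same section has staff record events that participants report or staff observe, at in-person contacts and at other times as applicable.

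Section 7 defines when a training symptom such as joint soreness, eye strain or headache counts: it must increase in frequency and "last more than 24 hours after participating in intervention exercises will be considered an adverse event".

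Section 6.3.1 plans contact within 3 days of an unexpected missed session, then two or three attempts a week for three weeks, then a letter. Of these contacts it says "Participants will be requested to schedule a make-up in-lab training session as soon as possible", and that staff will encourage return for post-test. Section 6.3 says "Reasons for ineligibility will be documented"; it sets no matching requirement for a voluntary stop.

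**The concern.** The plan's own definition needs a later contact. A question at the end of a session cannot establish that a symptom lasted more than 24 hours after it; the next session or post-test can. For the last attended session of someone who then misses post-test, neither takes place. If wrist or back pain from that session is the reason for stopping, nobody is scheduled to ask about it.

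Two things depend on the answer. For the participant, the advice to seek treatment (section 7) and the clinical follow-up and referral (section 11.2) start only once an event is identified. For the trial, section 9.5 assesses safety by comparing adverse-event counts between arms, without a formal monitoring plan or board, and a confirmed imbalance can lead to a decision on early termination. Those counts are less complete for people without a closing interview.

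**Working it through.** **Who is asked, and when**

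| Participant | Asked at each attended visit | Later question covering the last session |
|---|---|---|
| Continues training | yes | next session, then post-test |
| Stops, attends post-test | yes | post-test |
| Withdrawn for a listed medical event | yes | the triggering event is already known, recorded and followed up |
| Stops voluntarily, misses post-test | yes, until the last session | none planned |

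Only the last row is open.

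**Planned size.** Section 9.3 expects up to 20% attrition after the first in-person visit, with 450 screened in person for 360 completers. This reproduces: 360 / (1 − 0.20) = 450, so 90 do not complete. Some of the 90 would be lost before randomization. Section 9.5 expects 140 post-tests by the interim analysis. Assuming the 20% applied to randomized people, 140 / 0.80 = 175 randomized and 175 − 140 = 35 without a closing interview.

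**Size in the appended results.** Section 14 reports that 76% of randomized participants completed post-test and that 19 were excluded from analysis. The readable text does not state the number randomized, so it is inferred. The baseline tests have 266 error degrees of freedom for two groups: 266 + 2 = 268 people.

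- Reading A, 268 randomized: 0.76 × 268 = 204 post-tested; 268 − 204 = 64 not.
- Reading B, the 19 excluded are additional: 268 + 19 = 287 randomized; 198 analysed (Table 14.3) + 19 = 217 post-tested; 217 / 287 = 75.6%, consistent with 76%; 287 − 217 = 70 not.

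**How far these people were followed.** The expectations questionnaire is given at sessions 17 to 20, or at the start of post-test (section 6.1). Its test has 214 error degrees of freedom: 214 + 2 = 216 raters. Raters without post-test number at least 216 − 204 = 12 (A) or 216 − 198 = 18 (B). They had reached about session 17 and had been asked at each visit until then. At most 64 − 12 = 52 (A; 52 / 268 = 19.4%) or 70 − 18 = 52 (B; 52 / 287 = 18.1%) had neither a rating nor a post-test. Some of these may have left before any training.

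**Did post-test reach early stoppers?** Of the 198 analysed, 189 had 15 or more sessions (Table 14.3 and its note), so 198 − 189 = 9 had fewer. Counting everyone post-tested, the ceiling is 204 − 189 = 15 (A) or 217 − 189 = 28 (B). Either way, post-test reached few people who stopped early.

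**The case against.** The strongest reply is that little can escape. Staff ask at every session, so soreness that persists is caught at the next one. Someone who stops because of pain is called within days, and whatever they say is to be recorded. Expected events are mild, and section 7 states that earlier research on the interventions reported no serious adverse effects. The trainer procedure document cited in sections 5.7 and 6.1.2 is not supplied and may contain a harms question for these calls. Most of this stands and is why the gap is narrow. What remains is that the protocol does not require anyone to ask.

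Four stronger readings are tempting, and the documents do not support them.

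- *Events in withdrawn participants are lost.* The medical triggers in sections 5.7.1 and 8 are known to staff when they cause withdrawal; sections 11.1 and 11.2 have adverse events recorded, evaluated and followed up. Section 14 lists exclusions for head injury, anesthesia and hospitalization, so such events were learned of in practice.
- *Some 64 to 70 people had unrecorded harms.* The figure counts closing interviews not held. Under reading A, 75.5% to 76.5% of 268 gives 203 to 205 post-tested, so at most 205 − 198 = 7 of the 19 excluded could have been post-tested. At least 19 − 7 = 12 of the 64 then had an event already known. Reading B does not allow this inference.
- *The safety comparison is biased between arms, and nothing would reveal it.* No difference in capture by arm is shown. Section 9.5 also compares attrition and has significant differences in attrition or adverse events investigated further.
- *Reasons for stopping went unrecorded.* Section 6.3 plans a CONSORT chart and a status code that includes refusal. The chart is not shown, so what was recorded cannot be read here.

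**Conclusion.** The gap is real but narrow. It applies to participants who stop voluntarily and miss post-test, and to symptoms that begin, or come to meet the 24-hour definition, after the last attended session and are not volunteered. About 35 people might have lacked a closing interview at the interim on the planned rate, and roughly 64 to 70 did in the trial as reported. The first figure assumes that planned attrition applies after randomization; the second rests on a number randomized inferred from degrees of freedom. The number of missed harms and the split by arm cannot be determined from the documents. The efficacy analysis is unaffected. The change is worth making because it improves safety capture and the section 9.5 comparison at very little cost; confidence is medium because the trainer procedure document is unseen.

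**What to change.** - **Sections 6.3.1 and 11.1, missed-session contacts.** Have staff ask the existing adverse-event question and record the reason for stopping.
- **Same sections, close-out call.** Make one call to anyone who discontinues or misses post-test, by the end of the post-test window: 60 days after training completion, or 18 weeks after baseline if no session was attended. Section 6.1 gives no day limit for those with 1 to 15 sessions; 60 days after the last attended session would serve.
- **Who calls.** Trainers or the coordinator, who already know the assignment (section 5.5), so that testers stay blind.
- **Section 9.5.** Report by arm the number without a closing interview beside the adverse-event comparison.

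The cost is a few extra questions on calls already planned, one short call per non-returner (about 64 to 70 in a trial of this size), an IRB wording change and one line in the interim table. No new staff or instruments are needed. Data collection ended in April 2021 (section 14), so the calls apply to a continuation or successor protocol; the by-arm count of missing closing interviews can still be reported for this trial.

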11.2 Follow-up for Adverse Events

Research Assistants will monitor participants for any adverse events at study visits. At the post-test study visit, participants will be directly interviewed about any possible adverse events that occurred since their initial visit. A study physician and/or [name] will follow-up with the participant for any adverse events. The participant will be referred to proper treatment.

11.3 Safety Monitoring

The PI and the Study Physicians will be responsible for ensuring participants' safety.

[name] will perform analyses to monitor participant safety, evaluate the progress of the study, to review procedures for maintaining the confidentiality of data, the quality of data collection, management, and analyses.

All OHRP and local IRB requirements for reporting adverse events will be followed.

11.4 Confidentiality

All evaluation forms, reports, recordings, and other records that leave the site will be identified only by the participant id number to maintain subject confidentiality. All records will be kept in a locked file cabinet. All computer entry of data forms will be done using participant ids only and without participant names. Clinical information will not be released without written permission of the participant, except as necessary for monitoring by IRB, NIH, or the OHRP

11.5 Study Modification/Discontinuation

The study may be modified or discontinued at any time by the IRB, the NIH, the OHRP, or other government agencies as part of their duties to ensure that research subjects are protected.

Study Modifications

Date Implemented	Modification	Rationale
04/23/2018	For the pilot replicate, the FAS, Animals/ Boys' Names, and Fruits/ Furniture version will be administered at baseline and	The music listening condition involves a lesson on musical instruments. Thus, we decided that using this version of verbal

	also at post test.	fluency category switching at post would unfairly bias the active control condition. We did not realize this until during the training phase of the pilot replicate. We changed the order for future replicates such that Vegetables/Musical Instruments version is administered at baseline and the Fruits/Furniture version will be administered at post-test.
07/16/2018	Page 12, 5.2 Exclusion Criteria. We clarified that individuals who have previously participated in the USF Music Research and Testing Lab studies are excluded.	This was inadvertently omitted from the protocol version 1. All individuals screened for the study were excluded if they reported prior participation in the Music Research and Testing Lab. The rationale is such individuals would have completed similar or the same measures as administered in this study and may have received music training.
07/16/2018	Page 15, 5.7 Interventions Administration and Duration. We omitted the sentence that indicated a textbook will be provided and weekly homework will be assigned.	The study investigators met to discuss the study progress and any modifications needed since completion of the pilot replicate. The trainers and a Co-I noted that it was difficult to make the homework assignments and engagement equivalent across the two conditions. It was decided that we will omit the homework for replicate 1 and the remainder of the study. Participants will only access the textbooks during the in-lab training sessions. There is no evidence that homework is required for piano training to be efficacious. Ensuring equivalency of the two conditions is the rationale.
07/16/2018	Page 12, 5.2 Exclusion criteria. We added, "which interferes	The PI and study coordinator felt the exclusion criteria of any

	with ability to use a keyboard” to exclusion criteria regarding numbness or tingling.	numbness or tingling in any finger was too conservative and that individuals were being excluded that would be able to successfully participate in the study. We decided to add this phrase in an attempt to only exclude those who would not be able to successfully complete the intervention.
07/16/2018	Pages 13-14, 5.3 Enrollment Procedures. Those who score a 26 or better on the MoCA will be enrolled in the study (not 27). Those potentially eligible who score between 20 to 25 (not 26) on the MoCA who were not referred by the MDC or study physician will also complete a clinical evaluation visit.	The PI and Study Coordinator felt the criteria for clinical evaluation were too stringent. The study investigators decided to use the traditional cut-point of 26 for MoCA to determine who is eligible and who requires further evaluation.
07/30/2018	Page 14, 5.3 Enrollment Procedures. We clarify that clinically significant abnormalities are shared with the participants who are encouraged to seek treatment. We added the phrase, “that would likely interfere with their ability to benefit from intervention” regarding any significant clinical abnormalities.	This has been our procedure beginning in replicate 1. The goal is to be inclusive and to allow those who could potentially benefit from intervention to continue participation in the study.

The randomized groups did not differ in sex, $\chi^2(1)=.787, p=.375$, ethnicity $\chi^2(1)=.167, p=.683$, or race, $\chi^2(1)=.045, p=.832$. The Music Reading Assessment scores did not differ between the two groups, $t(266)=-.958, p=.338$. The randomized groups did not significantly differ in age, $F(1,266)=.293, p=.589$, education, $F(1,266)=.369, p=.544$, MoCA, $F(1,266)=.427, p=.514$, or GDS, $F(1,266)=.943, p=.332$. However, there were marginally significant group differences for PTA in the left ear, $F(1,266)=3.31, p=.070$ and statistically significant group differences for both PTA in the right ear, $F(1,266)=6.69, p=.010$, and visual acuity, $F(1,266)=8.99, p=.003$. The music listening group tended to have worse hearing, while the piano training group tended to have worse visual acuity. See Table 1. The groups also differed significantly in their expectations regarding potential benefits of their randomized group, $F(1,214)=15.07, p<.001$. The piano training group had an average rating of 5.55 while the music listening group had an average rating of 4.99, indicating the piano training condition had higher expectations about the potential effects of their randomized condition. The piano training group also rated their condition as more challenging with 92% agreeing that the intervention was challenging as compared to 86.3% of the music listening group indicating their condition was challenging ($p<.001$).

Principal component analysis with varimax rotation was conducted to reduce the number of variables for analyses. Please see Supplemental Table A for details. The first factor reflected cognitive performance speed and included the Trail Making Test, Digit Coding, and the TEA visual elevator and phone search subtests. The second factor included all three verbal fluency subtests. The third factor reflected CAP and included DDT, DSI, TCS, and WIN. The fourth factor included two indices from the TEA phone search while counting and visual elevator accuracy. The fifth composite included ATTR across- and within- channel performance. Baseline composites of cognitive performance, verbal fluency, ATTR, CAP, and everyday function were created by averaging z scores after the reverse-scaling of items with negative factor loadings. Post-test scores were standardized

by baseline means and *SDs*. Timed IADL performance did not significantly load on any factor and was thus examined separately.

In the primary analyses, we examined whether performance changed differentially by random assignment across composite outcomes from baseline to post-test as indicated by a significant group-by-time interaction. Covariates included hearing PTA, visual acuity, and expectations. The group-by-time interactions were not statistically significant for any of the outcomes ($ps > .194$). See Table 2. The results did not change when we included only those who were adherent ($ps > .180$). See Supplementary Table B. Piano training did not significantly enhance CAP, cognition, or everyday function as compared to music listening. We further examined if intervention effects varied by MCI status (Supplementary Table B). There were no significant group-by-time-by-MCI status interactions indicating those with and without MCI did not show differential benefit ($ps > .245$). Thus, MCI did not significantly moderate the effects of piano training.

Effect sizes for piano training as compared to music listening are shown in Table 3. Improvements were not evident in the primary analyses, adherent analyses, or the subsample without MCI on measures of CAP, cognition, or everyday function. Participants with MCI randomized to piano training showed potential small effect sizes for improvement relative to music listening on Trails A, Digit Symbol Coding, and one subtest of the TEA ($ds \geq 0.25$). Raincloud plots of individual assessment and composite variables are included in the supplemental materials.

Results indicated significant effects of time for ATTR in all models and significant effects of time for CAP in the primary and adherent analyses indicating improved performance from pre- to post- training. Significant effects of time were found for cognition and TEA in the primary and adherent analyses, indicating a tendency for decline across time. With respect to covariate effects, CAP, ATTR, and cognitive performance were significantly impacted by hearing. Similarly, Timed IADL and cognitive performance varied significantly by visual acuity. Those with poorer hearing or vision tended to perform worse on these outcomes. Interestingly,

expectations about the assigned condition were significantly related to composite outcomes of CAP and cognition. However, having greater expectations that the randomized condition would positively affect abilities was associated with poorer performance. See Table 2. Additional sensitivity analyses examined if there were differential effects by sex. No significant group-time-sex interactions were evident ($p > .119$), and the pattern of results was the same when analyses were stratified by sex.

Table 14.1. *Participant characteristics by randomized arm and cognitive status.*

Cognitive status	Piano Training		Music Listening	
	Non-MCI	MCI	Non-MCI	MCI
	M (SD)	M (SD)	M (SD)	M (SD)
	n (%)	n (%)	n (%)	n (%)
Age in years	69.1 (5.5)	71.4 (7.1)	69.6 (5.2)	72.1 (5.7)
Education in years	16.0 (2.3)	16.5 (2.2)	16.0 (2.1)	15.4 (2.3)
Sex (% female)	63 (65%)	18 (48%)	58 (59%)	17 (44%)
Music Reading Assessment score (/40)	2.52 (4.31)	2.43 (3.83)	3.42 (5.41)	2.08 (4.29)
Montreal Cognitive Assessment score (/30)	26.6 (2.1)	23.3 (1.4)	26.6 (1.9)	22.8 (1.6)
Geriatric Depression Scale short-form score (/15)	0.9 (1.2)	1.1 (1.1)	0.9 (1.1)	0.6 (0.9)
Pure tone average left ear (dB)+	19.8 (9.4)	20.4 (9.4)	20.9 (10.8)	27.7 (15.9)
Pure tone average right ear (dB)+*	18.6 (10.3)	20.4 (9.9)	22.4 (14.0)	25.8 (11.6)
Visual acuity (logMAR)+*	.04 (.12)	.09 (.15)	.01 (.13)	.01 (.10)
Expectations (rating/7)*	5.4 (1.2)	5.8 (0.8)	4.9 (0.8)	5.3 (0.8)

Note. MCI=mild cognitive impairment. +Lower scores reflect better performance. *Significant differences by randomized group were evident in pure tone average right ear, visual acuity, and expectations ($ps<.01$).

Table 14.2. *The effects of randomization to piano training as compared to music listening from baseline to post-training across composite outcomes of central auditory processing, cognition, and everyday function.*

	Estimate	SE	p	Estimate	SE	p
	ATTR+			Central auditory processing		
Intercept	53.90	1.17	<.001	46.25	0.73	<.001
Group	-2.24	2.37	.346	-1.72	1.49	.249
Time	-2.77	0.68	<.001	2.29	0.36	<.001
Group x time	1.51	1.35	.265	.465	0.71	.515
Hearing	0.12	0.06	.030	-0.63	0.04	<.001
Visual acuity	6.24	4.71	.187	-7.270	3.97	0.07
Expectations	0.79	0.59	.185	-1.20	0.49	.016
	Verbal fluency			Cognition		
Intercept	49.32	0.98	<.001	51.81	0.90	<.001
Group	-1.81	2.00	.367	-2.62	1.84	.157
Time	0.41	0.48	.393	-1.40	0.42	.001
Group x time	-0.29	0.96	.763	0.39	0.84	.638
Hearing	-0.09	0.06	.134	-0.14	0.06	.016
Visual acuity	-6.55	5.33	.220	-15.45	5.12	.003
Expectations	-0.79	0.67	.234	-1.96	0.64	.003
	Timed IADL+			Test of Everyday Attention		
Intercept	48.89	1.32	<.001	62.34	1.15	<.001

Group	3.15	2.67	.240	1.37	2.33	.557
Time	0.14	0.79	.863	-8.61	0.67	<.001
Group x time	-1.53	1.58	.327	-0.40	1.340	.765
Hearing	0.07	0.57	.194	-0.02	0.05	.603
Visual acuity	12.75	4.770	.008	0.24	4.470	.957
Expectations	1.02	0.59	.089	-0.79	0.56	.157

Note. ATTR=Adaptive Tests of Temporal Resolution, IADL=instrumental activities of daily living. MCI=mild cognitive impairment. +For ATTR and Timed IADL lower scores reflect better performance.

Table 14.3. *Effect sizes for piano training relative to music listening across composite outcomes and assessments for the analytic sample overall, among those adherent, and by cognitive status.*

Outcome Measure	d Effect Size			
	Overall (n =198)	Adherent (n =189)	Non-MCI (n =146)	MCI (n =52)
Central auditory processing composite	-0.01	-0.01	0.00	-0.07
Dichotic Digits	-0.06	-0.07	-0.03	-0.14
Dichotic Sentence Identification	0.01	0.01	0.02	-0.07
Time Compressed Speech	-0.01	0.01	0.03	-0.06
Words in noise	0.03	0.03	0.12	0.01
Adaptive Tests of Temporal Resolution composite	0.17	0.20	-0.09	0.24
Cognitive composite	-0.03	-0.03	-0.10	0.08
Trails A	0.03	0.06	0.00	0.43
Trails B	-0.17	-0.20	0.01	-0.54
Digit Symbol Coding	0.08	0.09	0.06	0.26
Test of Everyday Attention - Visual elevator timing subtest	0.02	0.02	0.03	0.44
Test of Everyday Attention - Telephone search time	-0.29	-0.32	0.08	-0.27
Verbal fluency composite	0.05	0.06	0.09	-0.12

Letter fluency	0.00	0.02	0.09	-0.36
Category fluency	0.18	0.20	0.18	0.13
Switching fluency	-0.06	-0.05	-0.07	-0.05
Test of Everyday Attention composite	0.04	0.08	-0.30	-0.02
Visual Elevator accuracy	0.01	0.03	-0.12	-0.19
Dual task decrement	0.10	0.13	-0.18	0.22
Timed Instrumental Activities of Daily Living composite	-0.15	-0.21	0.09	-0.13

Note. MCI=mild cognitive impairment. *d* effect sizes were calculated as pre- to post- change in the piano training condition relative to the music listening condition divided by the baseline standard deviation such that positive values would indicate improvement. Adherent analyses include those who completed 15 or more sessions of the assigned condition.
